# 10. EXPLORATORY EFFICACY ANALYSIS

Listings of efficacy parameters will be done for the ITT population. Summaries and analyses will primarily be done for the mITT population; some or all summaries and/or analyses may also be done for other analysis populations defined in [Section 6](#). In addition, “last observation” analyses will be done for certain parameters for which some subjects’ final assessments were done too late to be included in the Month 12 analysis window.

Unless otherwise noted, for the final analysis changes from baseline will be analyzed using general linear models with baseline values as covariates. Analyses of the effect of treatment group, time (baseline, Month 6, Month 12), and their interaction will be done using mixed effects linear regression, with subject as a random effect, time and treatment group as fixed effects, and baseline as a covariate. Study site may also be included as a random effect if there is evidence of correlation within study sites (per the interclass correlation coefficient from the unconditional model) and/or if doing so appreciably improves the model fit (e.g., per Akaike’s Information Criterion). Residuals will be evaluated for substantial departure from normality and independent and constant variance and appropriate remedies (e.g., data transformations, detecting and assessing the influence of outliers, alternative analytical approaches) will be attempted when necessary. An unstructured covariance will be the default covariance structure but other structures (e.g., compound symmetry) may be used to evaluate sensitivity to the choice of structure or, if necessary, to achieve convergence.

For the analysis of LV LGE rate of change since baseline compared to rate of change from historical MRI to baseline, rate of change  $RC(t_i)$  for time point  $t_i$ ,  $i = 1$  to 3 (baseline, Month 6, Month 12, respectively), will be calculated as

$$RC(t_i) = (X(t_i) - R(t_i)) / D(t_i)$$

where  $X(t_i)$  is observed LGE at  $t_i$ ,  $R(t_i)$  is observed LGE at the reference time point for  $t_i$ , and  $D(t_i)$  is the number of days between  $t_i$  and the reference time point for  $t_i$ . The reference time point will be the date of historical MRI for  $i = 1$  and baseline for  $i > 1$ . The mixed effects model to be used for the final analysis will be similar to that described above, with historical LGE included as a covariate. The LSMEANS procedure in PROC MIXED will be used to compare  $RC(t_2)$  and  $RC(t_3)$  to  $RC(t_1)$  within each treatment group, and tests for interaction along with descriptive statistics will be used to evaluate differences by treatment group.

Assuming missing observations are “missing at random” (MAR), i.e., the fact that they are missing is unrelated to the missing variable but can be related to another variable on which data have been collected, the maximum likelihood (ML) approach is able to handle subjects with either Month 6 or Month 12 changes from baseline missing, but not both. Therefore, for final analyses based on the mITT population, missing data will be addressed using ML. Final analyses based on the ITT population may include subjects with both Month 6 and Month 12 changes from baseline missing; under these circumstances, multiple imputation will be used based on all observations and will use a fully conditional specification method with 20 burn-in iterations and the regression method of imputation. Variables in the imputer’s model will be baseline observation (because baseline is used as a covariate in analyses), Month 6 change from baseline, Month 12 change from baseline, and treatment group. Because the MAR assumption is not testable, and because it seems possible that subjects with poorer outcome may be more likely to miss trial assessments, a sensitivity analysis under a “missing not at random” (MNAR) assumption may be done (for the final analysis only) for any efficacy endpoint for which all change from baseline measurements are missing for some subjects. For the MNAR model, multiple imputation will use the pattern-mixture model approach to address missing values; i.e., the imputation will be based on a pre-specified subset of subjects: for this MNAR analysis, only subjects randomized to usual care. Because very few missing observations are expected in this trial, 5 imputed data sets will be used for all analyses using multiple imputation.

For all analyses of all efficacy parameters, tests of treatment effect will be based on comparisons of least-squares (LS) means with no adjustment for multiple comparisons.

Efficacy parameters are described below.

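### SAP Section 10 makes baseline both a level of time and a covariate in the mixed model, in conflict with its own missing-data text; taken literally, the model either has no likelihood maximum or gives visit-level tests that generally miss 0.05

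*SAP*

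**What the plan says.** SAP Section 10 gives two analyses of efficacy parameters.

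- A change-score model: "changes from baseline will be analyzed using general linear models with baseline values as covariates".
- A mixed model: "Analyses of the effect of treatment group, time (baseline, Month 6, Month 12), and their interaction will be done using mixed effects linear regression". The SAP then lists what this model contains: "with subject as a random effect, time and treatment group as fixed effects, and baseline as a covariate".

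On covariance, "An unstructured covariance will be the default covariance structure but other structures (e.g., compound symmetry) may be used", either as a sensitivity check or to obtain convergence. Treatment tests compare LS means without multiplicity adjustment. SAP Section 7.3 sets two-sided 0.05.

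The missing-data paragraph of Section 10 describes different data. It says maximum likelihood is "able to handle subjects with either Month 6 or Month 12 changes from baseline missing, but not both", and that "for final analyses based on the mITT population, missing data will be addressed using ML". The imputation model contains "baseline observation (because baseline is used as a covariate in analyses), Month 6 change from baseline, Month 12 change from baseline, and treatment group". Baseline is a predictor there, and only two post-baseline changes are outcomes.

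For the LGE rate-of-change analysis, "The mixed effects model to be used for the final analysis will be similar to that described above, with historical LGE included as a covariate".

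**The concern.** SAP Section 7.6 defines baseline as the last value before infusion or the reference time point. In the three-level model, the baseline response and the baseline covariate are therefore the same number; if the response is change, the baseline response is zero for everyone. The baseline rows carry no residual variation, yet they enter the covariance estimate.

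Two things are at stake. First, if the default model cannot be fitted, a replacement will be picked once the data are in hand, and by then the Month 6 top-line results are to be public (SAP Section 13.2.2). Second, if the replacement is compound symmetry with baseline rows kept, standard errors at Month 6 and Month 12 rest on a variance that is averaged with rows of zero variance.

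**Working it through.** **Inputs from the documents.** Two-sided 0.05 (SAP 7.3); about 12 per arm, at most 30 randomised 1:1 (SAP 3 and 4); time levels, covariate and covariance structures (SAP 10).

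**Assumed, because the documents give no SD, slope or correlation.** Baseline SD 1.5; Month 6 change SD 1; slope of change on baseline -0.1 to -0.5, so the correlation r of baseline with change runs from -0.15 to -0.75; correlation of the two changes 0.3, 0.5, 0.7, 0.85; Month 12/Month 6 SD ratio 1, 1.25, 1.5. That is 5 x 4 x 3 = 60 settings, with 20,000 null trials each (Monte Carlo SE about 0.002) and complete data.

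**1. The plan's own figure.** Per-visit change-from-baseline ANCOVA gives type I error 0.047 to 0.053 throughout. The nominal 0.05 is reproduced for that model.

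**2. Baseline rows.** Write Y(i,t) = m(g,t) + b·B(i) + e(i,t) for t = baseline, Month 6, Month 12.

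- Response is change: Y = 0 at baseline, so b = 0 and m = 0 give zero residuals.
- Response is the observed value: Y = B at baseline, so b = 1 and m = 0 give zero residuals.

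**3. Three-by-three unstructured covariance.** With those residuals at zero, the log-likelihood grows as -(n/2)·log(s0) under ML and -((n-3)/2)·log(s0) under REML, where s0 is the baseline residual variance. For n = 24, each hundredfold fall in s0 adds 12 x 4.605 = 55.3 (ML) or 10.5 x 4.605 = 48.4 (REML):

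| s0 | 1 | 1e-2 | 1e-4 | 1e-6 | 1e-8 |
|---|---|---|---|---|---|
| ML | -93.5 | -38.2 | 17.0 | 72.3 | 127.6 |
| REML | -98.2 | -49.8 | -1.4 | 46.9 | 95.3 |

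There is no maximum. Change and observed-value responses give the same figures. This step does not depend on the assumed variances. A fit that collapses to the unadjusted change still holds 0.047 to 0.053, but its variance is larger by 1/(1-r²), from 1.02 at r = -0.15 to 2.29 at r = -0.75.

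**4. Compound symmetry, large-sample check at zero slope.** The pooled variance is (0 + v6 + v12)/3, while the test at visit t needs v(t). The type I error is 2·[1 - Φ(1.96·√(((v6+v12)/3)/v(t)))].

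- v12 = v6: 1.96·√(2/3) = 1.600, giving 0.110 at both visits.
- v12 = 2·v6: Month 6 0.050; Month 12 1.96·√(1/2) = 1.386, giving 0.166.
- v12 = 3·v6: Month 6 0.024; Month 12 0.191.

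**5. Compound symmetry, simulation, 12 per arm, REML, equal SDs, both visits.**

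| r | Baseline rows kept |
|---|---|
| -0.15 to -0.30 | 0.102 to 0.113 |
| -0.45 | 0.095 to 0.101 |
| -0.60 | 0.083 to 0.091 |
| -0.75 | 0.068 to 0.074 |

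Without baseline rows the range is 0.042 to 0.051. Full ML with baseline rows runs from 0.120 to 0.136 at the weakest r down to 0.082 to 0.091 at r = -0.75; without them it is 0.054 to 0.066.

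**6. Unequal SDs, REML.**

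| Month 12/Month 6 SD | Month 12, rows kept | Month 6, rows kept | Month 12, rows removed |
|---|---|---|---|
| 1.25 | 0.134 to 0.148 | 0.028 to 0.072 | 0.068 to 0.090 |
| 1.5 | 0.164 to 0.174 | 0.013 to 0.046 | 0.086 to 0.111 |

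Part of this error is due to compound symmetry itself, since it remains after the baseline rows are removed.

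**7. Other tests from the same model, REML.** In 55 settings the group main effect is 0.028 to 0.053 and the interaction F test 0.048 to 0.071. In the other 5 (r of -0.60 or -0.75 with correlation of changes 0.3 or 0.5), the main effect is 0.000 to 0.020 and the interaction 0.067 to 0.104.

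**The case against.** The strongest reply is that this is a drafting slip. The missing-data text, the imputation model and the results tables all concern post-baseline changes, so a two-level time factor was probably meant. The three levels may belong to the LGE rate analysis that follows, where the baseline level is a real historical rate. Compound symmetry is only an example, and the planned residual check should expose a time level with no variance. No per-visit contrast from the mixed model is named; visit-level LS means are the natural reading because SAP Section 2.3.2 assesses endpoints at 6 and 12 months.

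Most of that stands, and it limits the reach. It does not remove the conflict. The missing-data text does not override the three-level sentence, SAP Section 15 does not mention it, and the remedy after a failed residual check is left open.

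A reader might infer that the default fit must fail on any reading. It need not: Section 10 never says residual covariance. If unstructured refers to a single random intercept, the fit has a maximum, but the model is then compound symmetry with the error shown above. The contrast with compound symmetry makes the residual reading more likely.

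A reader might also infer that the LGE rate model is degenerate, or that baseline and historical LGE must not both be covariates. Neither is shown. The interval between the historical scan and baseline may differ between subjects, so the two values need not determine the historical rate exactly.

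**Conclusion.** The point holds as a conflict within SAP Section 10 that should be fixed before the final analysis. On the likely reading, the default model has no maximum under ML or REML, whatever the variances. On the other reading, or with compound symmetry as the substitute, visit-level tests with baseline rows kept generally miss 0.05: about 0.07 to 0.11 per visit at equal SDs, and more at Month 12 when its SD is larger, with Month 6 then sometimes conservative. These sizes rest on assumed SDs, slopes and correlations. They are not universal: at a standardised slope of about -1.73 with equal variances the error is 0.051 and 0.054, and at -3 it is 0.026.

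It would be wrong to conclude that the plan's efficacy p-values are inflated in general. The change-score model holds 0.05, the group main effect is not inflated, and efficacy is exploratory. It would be equally wrong to call the interaction test safe throughout: it is near 0.05 in most assumed settings but reaches about 0.07 to 0.10 when regression to the mean is strong and the changes are weakly correlated.

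**What to change.** Reconcile the two parts of Section 10. In the mixed model:

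- take the Month 6 and Month 12 changes as the only outcomes, so that time has two levels;
- include treatment, time, treatment-by-time and baseline as a covariate;
- use an unstructured residual covariance with no separate subject random effect, which is not identifiable beside it;
- fit by REML with a stated small-sample degrees-of-freedom method, for example Kenward-Roger. REML handles a missing Month 6 or Month 12 value under MAR as ML does.

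Naming REML matters. With this two-level model, 12 per arm, 4,000 null trials per setting and 21 degrees of freedom, full ML gave 0.054 to 0.068 and REML 0.044 to 0.056 over four assumed settings.

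Alternatively, keep three time levels with the observed value as response, constrain the arms to a common baseline mean, and drop baseline as a covariate.

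For the LGE rate model, at most state which covariates it uses.

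The cost is one or two sentences and no extra data. Some visit-level p-values will be larger than under compound symmetry with baseline rows kept.

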## **6.8 Magnetic Resonance Imaging**

All subjects will undergo contrast-enhanced MRI at screening and the Month 6 and 12 study visits (or, Early Termination Visit). It is anticipated that the duration of each MRI session will be 45-60 minutes. Acquisition parameters and techniques are specified in the MRI Imaging Manual. The site-based MRI technologists will be trained and certified in the common acquisition protocol prior to initiation of enrollment at each site.

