## 6.9 Clinical Function and Quality of Life Measures

At the screening, 6 Weeks, 3 Months, 6 Months, and 12 Months (or Early Termination) study visits, the subject will be asked to complete the Performance of Upper Limb (PUL) assessment and spirometry. Both the subject and the parent/guardian will be asked to complete the Pediatric Quality of Life Inventory (PedsQL) and the PODCI Adolescent Questionnaire (PODCI).

In addition, subjects assessed by the Investigator as capable of performing the Six Minute Walk Test (6MWT) will do so at screening, 6 Weeks, 3 Months, 6 Months, and 12 Months (or, Early Termination) study visits. Subjects unable to perform the Six Minute Walk Test at screening will not be required to perform the test at any subsequent visit.

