### **2.3.2 Exploratory Efficacy Endpoints**

The following exploratory efficacy endpoints will be assessed at 6 and 12 months post infusion or reference date:

- 1) Change from baseline in cardiac structural parameters measured by magnetic resonance imaging (MRI), including:
  - LV late gadolinium enhancement (LGE) expressed as a percent of LV mass
  - LV LGE expressed in grams
  - LV viable mass expressed in grams
  - Number of LV segments with LGE
  - LV circumferential strain
  - Left ventricular ejection fraction (LVEF)
  - LV end diastolic volume (LVEDV) and LV end systolic volume (LVESV)
  - LV stroke volume
  - Regional LV function assessment

LGE and circumferential strain will be assessed both overall as well as by individual segment and by groups of segments (e.g., infusion location, septum, base, LV free wall).

- 2) Rate of change since baseline compared to rate of change from historical MRI to baseline in LV LGE (overall and by individual segment and groups of segments)
  - expressed as a percent of LV mass
  - expressed in grams
- 3) Change from baseline in functional parameters:
  - Performance of Upper Limb (PUL) scale
  - Spirometry
  - 6-minute walk test (6MWT) in ambulatory patients
- 4) Change from baseline quality of life (QoL) parameters:
  - Pediatric Quality of Life Inventory (PedsQL), including the cardiac module
  - Pediatric Outcomes Data Collection Instrument (PODCI) Adolescent Questionnaire
- 5) Change from baseline in biomarkers:
  - Osteopontin
  - ST2
  - Interleukin 10 (IL-10)
  - Galectin-3

[figure not shown]

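### The collected Week 6 and Month 3 values of the functional and quality-of-life measures are left out of the SAP's mixed and imputation models, which can bias the Month 12 contrast if early dropout is unequal between arms

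*SAP*

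**What the plan says.** SAP Section 10 sets one longitudinal model for all efficacy parameters unless a later subsection says otherwise. Time enters as "time (baseline, Month 6, Month 12", with baseline as a covariate and an unstructured covariance as default. Sections 10.2 and 10.3 name no other visits for PUL, spirometry, 6MWT, PedsQL or PODCI.

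The imputation model contains "baseline observation (because baseline is used as a covariate in analyses), Month 6 change from baseline, Month 12 change from baseline, and treatment group".

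Protocol Section 6.9 schedules PUL, spirometry and the two questionnaires more densely: "At the screening, 6 Weeks, 3 Months, 6 Months, and 12 Months (or Early Termination) study visits, the subject will be asked to complete" them. For the 6MWT, subjects judged capable "will do so at screening, 6 Weeks, 3 Months, 6 Months, and 12 Months (or, Early Termination) study visits". MRI differs: "All subjects will undergo contrast-enhanced MRI at screening and the Month 6 and 12 study visits" (Protocol Section 6.8).

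On missing data, SAP Section 10 says that maximum likelihood is "able to handle subjects with either Month 6 or Month 12 changes from baseline missing, but not both", and concludes that it therefore suits the mITT. SAP Section 6 admits to the mITT any safety-population subject with a single post-baseline value of the parameter, at whatever visit.

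**The concern.** The time set matches the MRI schedule and is applied unchanged to outcomes with two more post-baseline visits. This has two consequences.

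First, the SAP's reasoning about the mITT does not hold for these outcomes. A subject with only a Week 6 or Month 3 value belongs to the mITT but lacks both Month 6 and Month 12, which is the case the SAP says maximum likelihood cannot handle. Withdrawal assessments on days 62 to 153 fall in the Month 3 analysis window (SAP Section 7.7), so they are outside both models too.

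Second, the missing-at-random assumption is made harder to meet than it need be. The SAP allows missingness to depend on other recorded data, and accepts that subjects doing worse may miss more assessments. Week 6 and Month 3 values are where early worsening would show, and neither model conditions on them. The trial is open-label, so unequal retention is plausible. What is at stake is the Month 12 contrast, for which p-values are planned.

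**Working it through.** The documents give no effect size, standard deviation or dropout rate for these outcomes, so there is no figure of the plan to reproduce. The sizes below rest on stated assumptions.

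**1. Mechanism.** A subject lost after Month 3 has no response in the two-visit model, which for such subjects is a complete-case analysis given baseline and arm. Let Δ be the amount by which the mean Month 3 value of those retained exceeds that of all subjects in an arm, given baseline. Let γ be the slope of Month 12 on Month 3 given baseline. Then approximately

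bias of contrast = γ × (Δ in one arm − Δ in the other).

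Equal Δ cancels. A model that contains Month 3 conditions on the driver of dropout, and the bias goes.

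**2. Numbers, deterministic dropout.** Assumptions: 12 per arm, no true effect, subject slopes with SD 1 over 12 months, noise SD 0.4 (variance 0.16) with correlation 0.5 between visits, and loss of the worst Month 3 values. The unit is the SD of the 12-month slopes.

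- Variance of Month 3 given baseline: 0.25² + 0.16 × (1 − 0.5²) = 0.0625 + 0.12 = 0.1825, so SD 0.427.
- Covariance of Months 3 and 12 given baseline: 0.25 + 0.16 × (0.5 − 0.25) = 0.29.
- γ = 0.29 / 0.1825 = 1.59.
- The three lowest of 12 normal scores have expectations −1.63, −1.12 and −0.79. Removing them raises the mean of the other nine by 3.54 / 9 = 0.393 SD. Removing only the lowest raises the mean of the other eleven by 1.63 / 11 = 0.148 SD.
- 3 v 0: 1.59 × 0.427 × 0.393 = 0.27.
- 1 v 0: 1.59 × 0.427 × 0.148 = 0.10.
- 3 v 1: 0.27 − 0.10 = 0.17.

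Simulation of the same set-up, repeated independently, gives these absolute biases (ranges are across runs):

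| Dropouts per arm | Months 6 and 12 only | All four visits |
|---|---|---|
| Complete data | about 0 | the same |
| 1 v 1 | 0.01 | 0.01 |
| 3 v 3 | 0.00 | 0.00 |
| 1 v 0 | 0.09–0.10 (0.2 SE) | at most 0.02 |
| 3 v 1 | 0.16–0.19 (about 0.35 SE or a little more) | at most 0.02 |
| 3 v 0 | 0.25–0.28 (0.5–0.6 SE) | at most 0.02 |

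Losing the worst decliners from usual care understates a benefit of CAP-1002; losing them from the CAP-1002 arm overstates it.

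**3. Numbers, graded dropout.** Assumptions: visit correlation 0.6 or 0.8 (AR(1)) or a random-slope model, usual-care decline of 0.5 SD a year, and dropout after Month 3 with log-odds 1.5 per SD of Month 3 decline. Estimation is by maximum likelihood with unstructured covariance. Absolute bias of the two-visit model, in outcome SDs, by overall dropout rate:

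| Dropout linked to decline | 5% | 10% | 20% | 30% |
|---|---|---|---|---|
| In usual care only | 0.02–0.04 | 0.04–0.08 | 0.07–0.13 | 0.10–0.17 |

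With the same mechanism in both arms and a true effect of 0.5 SD, it is about 0.01 to 0.05. With the same mechanism and no effect, or with a Month 6 value before dropout, it is about zero. With all four visits it is at most 0.01 throughout. At 12 per arm and 20% dropout linked to decline in usual care, the bias is 0.13 against a standard error of 0.43, or 0.13 / 0.43 = 0.3 SE.

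**4. Price of the larger model.** An unstructured matrix has k(k + 1)/2 parameters: 2 × 3 / 2 = 3 for two post-baseline visits and 4 × 5 / 2 = 10 for four, from about 24 subjects. The one fallback that SAP Section 10 names is compound symmetry. With the step 2 data, complete and with no effect, compound symmetry gives a Month 12 type I error of about 19% with four visits and 10% with two, because it pools the small early variances into the Month 12 standard error.

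**The case against.** The case for leaving the plan alone has several parts.

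- **The bias is conditional.** A reader might infer that any dropout driven by early decline biases the contrast. The documents do not support that: they give no dropout rate or pattern, and the calculation shows that equal dropout with no effect shifts both arms alike and cancels. This stands.
- **Three against none is severe.** It removes the worst quarter of one arm (3 / 12) and nobody from the other, while the SAP expects hardly any missing values. This stands; one against none is the more relevant row.
- **The early-termination visit rescues some subjects.** The Month 12 battery is attempted at withdrawal, and values from day 154 onward reach the Month 6 or Month 12 window. This narrows the problem to withdrawals before day 154 and those without that visit.
- **The endpoints are set at Months 6 and 12.** SAP Section 2.3.2 says so: "The following exploratory efficacy endpoints will be assessed at 6 and 12 months post infusion or reference date". That fixes what is reported, not which visits may inform the model.
- **The early values are not thrown away.** A reader might infer that they are, but SAP Section 7.2.1 presents summaries and analyses by visit window. They are absent only from the longitudinal and imputation models.
- **The imputation is said to use all observations.** The variables are then listed, and Week 6 and Month 3 are not among them.

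**Conclusion.** The omission and the faulty mITT reasoning are plain in the text. The bias is a possibility rather than a certainty. It needs dropout before Month 6 that depends on early decline and is unequal between arms, or such dropout together with a real treatment effect. Under the assumed models it runs from about 0.2 standard errors (one dropout against none) to 0.5 to 0.6 (three against none). Outside those conditions it is about zero. MRI endpoints are unaffected, because no Week 6 or Month 3 scan exists.

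The point is minor: these are exploratory endpoints in a trial whose primary objective is safety, and few missing values are expected. The sizes depend on assumed correlations and dropout mechanisms that the documents neither give nor contradict.

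**What to change.** For PUL, spirometry, 6MWT, PedsQL and PODCI, amend SAP Section 10 as follows.

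1. Use Week 6, Month 3, Month 6 and Month 12 as the post-baseline time levels, with baseline as a covariate. Keep Months 6 and 12 as the reported contrasts.
2. Add the Week 6 and Month 3 changes to the imputation model.
3. Correct the statement that implies every mITT subject has a Month 6 or Month 12 value.
4. Pre-specify a fallback covariance that lets variances differ by visit, such as heterogeneous Toeplitz or ARH(1), in place of homogeneous compound symmetry, with Kenward-Roger degrees of freedom.

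No new visit or measurement is needed. It is a cheap change but not a costless one: the unstructured covariance grows from 3 to 10 parameters for about 24 subjects, and fewer for the 6MWT, so the fallback may well be used. That is why item 4 belongs with the others.

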### 4.2 Inclusion Criteria

Each subject must meet all of the following inclusion criteria to be randomized in the study:

1. Male subjects 18 years of age or older must be able to provide informed consent and follow up with protocol procedures. Male subjects at least 12 years of age but younger than 18 years of age must be able to provide assent with parent or guardian providing permission for study participation. Only male subjects will be randomized into this study.
2. Documented diagnosis of Duchenne Muscular Dystrophy by genetic mutation analysis.
3. Cardiomyopathy with left ventricular scar by LGE in at least 4 segments as assessed by contrast-enhanced MRI, and EF >35% at the time of screening.
4. Use of evidence based medical-therapy in accordance with the “DMD Care Considerations Working Group” guidelines for the management of DMD, for at least three months prior to signing the consent form (or, providing assent) or documented contraindication or intolerance or patient preference.
5. Subjects must be taking systemic glucocorticoids for at least six months prior to screening.
6. Subjects must be 12 years of age or older at screening.
7. Subjects must be appropriate candidates for cardiac catheterization and intracoronary infusion of CAP-1002, in the judgement of the site’s interventional cardiologist.

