## 7.6 Study Period and Time Point Definitions

The following study periods and time points are defined:

Screening Period: the 30-day time period before IP infusion or the reference time point.

Baseline: for a given parameter for a given subject, the last observation before IP infusion or the reference time point.

Day 0: for a given subject, the day of planned IP infusion or the reference day.

(Nominal Visit) Analysis Time Point: analysis based on data collected at the *(nominal visit)* time point, where nominal visits are as shown below in [Section 7.7](#).

End of Study (EOS), Subject Level: subject-level EOS is reached after completion of the Month 12 visit or discontinuation for any reason.

EOS, Study-Level: EOS is reached when all randomized subjects have either completed the Month 12 visit or have discontinued from the study for any reason.

Long-Term Follow-Up (LTFUP) Period, Subject-Level: the LTFUP period begins after completion of the Month 12 visit and continues until 4 more annual visits have been completed.

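### The within-arm tests of LGE rate after versus before baseline can show slowing with no treatment effect, because the shared baseline scan also decides entry; inference should rest on between-arm comparisons

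*SAP*

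**What the plan says.** SAP 2.3.2 lists as an exploratory endpoint "Rate of change since baseline compared to rate of change from historical MRI to baseline in LV LGE", as a percent of LV mass and in grams, overall and by segment and segment group.

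SAP 10 defines each rate RC as observed LGE minus LGE at a reference scan, divided by the days between them. "The reference time point will be the date of historical MRI for" the first rate, RC(t1), and baseline for RC(t2) (Month 6) and RC(t3) (Month 12). "The LSMEANS procedure in PROC MIXED will be used to compare" RC(t2) and RC(t3) with RC(t1) "within each treatment group, and tests for interaction along with descriptive statistics will be used to evaluate differences by treatment group". Tests are two-sided at 0.05 (SAP 7.3), with no multiplicity adjustment (SAP 10).

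Four other provisions matter:
- **Baseline.** SAP 7.6 defines it as "for a given parameter for a given subject, the last observation before IP infusion or the reference time point". Protocol 6.8 says "All subjects will undergo contrast-enhanced MRI at screening and the Month 6 and 12 study visits", so the baseline scan is the screening scan.
- **Entry.** Protocol 4.2 requires "left ventricular scar by LGE in at least 4 segments as assessed by contrast-enhanced MRI, and EF >35% at the time of screening".
- **Historical scan.** Under Protocol 6.8.4 it is optional, must be at least 6 weeks old, and has no LGE threshold.
- **Other between-arm test.** SAP 10.1 plans treatment-group p-values for change from baseline in the MRI parameters, which include LGE.

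Neither document cautions about regression to the mean in the within-arm contrasts.

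**The concern.** The baseline value enters RC(t1) with a plus sign and RC(t2) and RC(t3) with a minus sign. If subjects are admitted partly because that scan read high, the pre-baseline rate is inflated and the post-baseline rates are deflated. Scar growth then seems to slow after entry in both arms, whatever the treatment does.

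A within-arm test cannot separate this from a treatment effect. With about 12 subjects per arm, chance can easily make the common drift significant in one arm only. The SAP does not say that significance in CAP-1002 alone is not evidence of benefit, and it does not rank the between-arm test above the within-arm ones.

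**Working it through.** The plan states no effect size, SD, power or error rate for this endpoint, so there is no figure to reproduce. The intervals and the 0.05 level come from the documents or are set near them. The LGE variability, the share screened out and the error correlation are assumptions.

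**Direction.** Let e be the error of the baseline scan, D1 the historical-to-baseline interval and D the baseline-to-follow-up interval. With a constant true slope,

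E[RC(t) − RC(t1)] = −E[e | admitted] × (1/D1 + 1/D).

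This is zero if admission does not depend on e. Sharing the scan therefore does not bias the mean by itself. Selection on the scan does, and sharing then counts the error twice.

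**Worked example** (percent of LV mass). Assume scan error SD 3, between-subject SD 5, 30% screened out on observed baseline LGE, and a true slope of 2.0 per year in everyone on average.
- E[e | admitted] = 3²/√(5² + 3²) × φ(−0.524)/0.70 = 1.543 × 0.497 = 0.77.
- D1 = 180 days = 0.493 year: 0.77/0.493 = 1.56, so the pre-baseline rate appears as 3.6.
- Month 6 (0.493 year): 2.0 − 1.56 = 0.4.
- Month 12 (0.986 year): 2.0 − 0.78 = 1.2.
- With D1 = 42 days (0.115 year), the shortest allowed, the pre-baseline rate appears as 8.7.

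**Noise grows with bias.** For D1 = D = 0.5 year the contrast is 2 × (Month 6 − 2 × baseline + historical). Its error variance is 4 × (1 + 4 + 1) = 24 times the scan variance, so its SD is 4.9 times the scan SD. Scan error large enough to produce marked slowing also makes the test noisy, so the two cannot be chosen separately.

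**Null simulations, moderate range.** Between-subject SD 8, scan SD 1 to 3, 40% to 80% passing, D1 0.5 to 1 year, selection variable correlated 0.8 with observed baseline LGE, 10 per arm.
- Scan SD 1: slowing 0.07 to 0.38 per year, contrast SD 2.4 to 4.9.
- Scan SD 3 with 40% passing: slowing 1.6 to 3.2 per year, contrast SD 7.2 to 14.4.
- CAP-1002 significant and usual care not: 2.6% to 8.5% across settings, against about 2.4% with no bias.

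**Null simulations, wider range.** 12 per arm, D1 = 180 days, Month 6. Correlation here is between the eligibility-reading error and the baseline LGE error. The nominal one-arm rate in the slowing direction is 2.5%.

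| Error SD / between-subject SD / correlation | Screened out | Slowing significant in one given arm | CAP-1002 only |
|---|---|---|---|
| 3 / 5 / 1 | 0% | 2.6% | 2.4% |
| 3 / 5 / 1 | 30% | 9.8% | 8.9% |
| 3 / 5 / 1 | 50% | 19.8% | 15.6% |
| 1.5 / 8 / 1 | 30%, 50% | 4.4%, 5.8% | 4.1%, 4.5% |
| 3 / 5 / 0.5 | 30%, 50% | 5.0%, 8.0% | 5.1%, 7.3% |
| 3 / 5 / 0 | 30%, 50% | 2.6%, 2.8% | 2.4%, 3.0% |
| 5 / 5 / 1 | 30%, 50% | 15.8%, 37.3% | 13.4%, 24.2% |

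An independent rerun of both sets agreed to within about one percentage point. The between-arm test of the rate change rejected in 4.4% to 5.8% of null trials in every setting of the wider set. Selection precedes randomisation, so its effect cancels between arms.

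The tests are complete-data t-tests standing in for the mixed-model contrasts. The historical-LGE covariate was left out; as a main effect with complete data it does not move a within-arm contrast over time.

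**Choice of between-arm test.** With 12 per arm, error SD 3 and a true rate difference of 4 per year, the direct comparison of RC(t3) has about 57% power. The difference in rate change has 5%, 13% and 25% at D1 = 42, 180 and 365 days.

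**The case against.** The strongest reply is that the valid test is already there. The same SAP sentence assigns differences by treatment group to interaction tests, and SAP 10.1 adds between-arm p-values for LGE change from baseline. That stands. A reader might infer that the endpoint has no sound between-arm test, or that only the interaction removes the bias. Neither is supported: any randomised between-arm comparison removes it.

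Second, the bias is conditional. Entry uses a segment count while the endpoint is in percent or grams. If the two readings share no error, or few candidates lie near 4 segments, there is little or no bias. That also stands.

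Third, SAP 10.1 plans informed reading, with earlier images in view. Error carried from the baseline to the follow-up reading would cancel in RC(t2) and RC(t3), removing the 1/D term. The 1/D1 term would remain unless the historical reading carried the same error, and the SAP does not say how that scan is read.

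Fourth, a reader might pair a slowing of 2 points per year with a contrast SD of 4 and conclude that one-arm-only significance occurs in about 21% of null trials. Those inputs do not belong together: in the moderate range, slowing that large comes with a contrast SD well above 4.

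Finally, the endpoint is exploratory and one of many. That limits the weight of the point, but not the case for removing a p-value that can mislead.

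**Conclusion.** The point holds for the within-arm contrasts only. They can show slowing in both arms with no treatment effect, because the scan that joins the two rates also decides entry. The direction follows from the definitions; the size cannot be fixed from the documents.

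Under the moderate assumptions, significance in CAP-1002 alone occurs in about 3% to 9% of null trials, against about 2.4% without bias. It is about 16% if half of candidates are screened out with fully shared reading error, and about 24% in the most extreme setting run, where scan error is as large as the between-subject spread. With unrelated reading errors there is no excess. The documents do not support calling this a frequent false finding, nor calling the planned between-arm tests biased. It is a modest defect that is cheap to correct.

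**What to change.** In SAP 10, for the LGE rate endpoint:
- Report RC(t2) − RC(t1) and RC(t3) − RC(t1) within each arm as estimates with confidence intervals and no p-values. Add a note that they include regression to the mean and that significance in one arm only is not evidence of effect.
- Base inference on the direct between-arm comparison of RC(t2) and RC(t3), adjusted for baseline LGE. Leave historical LGE out of this model, so that every subject with the follow-up scan contributes, with or without a historical scan.
- Keep the planned treatment-by-period interaction as supportive, in subjects with a historical scan. Making it the sole test would choose the weaker contrast in a subset.

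The cost is SAP wording and the loss of the within-arm p-values on an exploratory endpoint. No data collection or design element changes.
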